8.2 ALLOCATION AND BLINDING

This study is an open-label study with consecutive enrolment without randomization. There is no control group. Although there are two groups one hip and one shoulder group blinding of the surgeon is not applicable due to the different indications and product specificities. The evaluator will be blinded to the treatment groups.

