9.1.2 Visit 1: Pre-Operative Visit

- Obtain written informed consent from the subject as detailed in Section 7.5
----- Do not proceed until consent has been obtained -----
- Obtain demographic information and medical history, including information on all concomitant medications/therapies
- Screen the subject for protocol inclusion/exclusion criteria
- Assign the subject a study number and instruct the subject on treatment procedures
- Complete Screening and Enrollment Log
- Complete VAS-Scale for Pain for all subjects*
- Complete EQ-5D questionnaire for all subjects*
- Complete ROWE Score for shoulder*
- ASES Score for shoulder*
- Complete Constant-Murley Score for shoulder*
- Complete HOOS-ADE Score for hip*
- Complete Modified HSS Score for hip*
- Perform MRI, only in case of repair failure
- If any adverse events are observed or reported, they must be recorded as instructed in Section 12.3, adverse events and device deficiencies
- Complete Pre-Operative Visit CRFs

**Patient Reported Outcomes (PROs) are optional and used according to the surgeon's preference.*

Study Protocol—Device	 smith&nephew
Prospective, Multicenter, Post-Market Clinical Follow-up Study to evaluate safety and performance of the SUTUREFIX ULTRA and SUTUREFIX CURVED Suture Anchors in shoulder and hip arthroscopic repair	Number: 17-5010-06
	Version: 1.0, 09/MAY/2018
	Page: Page 40 of 87

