10.4.2 Analysis of Secondary Endpoint(s)

- Intra-operative anchor deployment success rate
- Number of anchors pulled out
- Use of additional anchors as a result of intra operative failure
- Device-related re-intervention

All the above variables will be categorical in nature hence frequencies together with percentages will be tabulated for the entire sample as well as by device implanted (SUTUREFIX ULTRA and SUTUREFIX CURVED) as well as the position, i.e. the hip or the shoulder will be reported.

All subjects

Clinical success rate, defined as subjects without signs of failure and/or re-intervention at 12 months; surgeon assessment

- The frequency of the subjects without a signs of failure and/or re-intervention at 12 months together with percentage with a 95% CI will be reported. Clinical success rate for the entire sample, by device implanted (SUTUREFIX ULTRA and SUTUREFIX CURVED) as well as the position, i.e. the hip or the shoulder will be reported. A binary variable of success/failure will be used to fit a logistic model adjusting device implanted and position to estimate the odds ratio of success if data allows.
- Subject pain assessed with a VAS at 6 months* and 12 months*

Study Protocol—Device	 smith&nephew
Prospective, Multicenter, Post-Market Clinical Follow-up Study to evaluate safety and performance of the SUTUREFIX ULTRA and SUTUREFIX CURVED Suture Anchors in shoulder and hip arthroscopic repair	Number: 17-5010-06
	Version: 1.0, 09/MAY/2018
	Page: Page 48 of 87

- Subject satisfaction assessed with a VAS at 6 months* and 12 months*
- EQ-5D Questionnaire at 6 months* and 12 months*
 - The VAS and EQ-5D-5L scores at different time points and end of study for the entire sample, by device implanted (SUTUREFIX ULTRA and SUTUREFIX CURVED) as well as the position, i.e. the hip or the shoulder will be summarized using mean, median, SD, minimum, and maximum. A one sample t-test will be used to test the difference between baseline and end of study scores. A non-parametric test will be considered if necessary.
- EQ-5D-5L

Based on the subjects responses (no problems/some or moderate problems/extreme problems) to each dimension (mobility, self-care, usual activities, pain/discomfort and anxiety/depression) an index utility score is calculated to represent the overall EQ-5D-5L score for each subject.

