The subject responses to each dimension score and the overall EQ-5D-5L index utility scores and EQ VAS scores will be summarized at baseline and all post-operative visits for the entire sample, by device type implanted and as well as the position, i.e. the hip or the shoulder.. The change in EQ-5D-5L index utility score and the change in EQ VAS score between baseline and all post-op visits will also be summarised.

EQ-5D-5L Utility scores and EQ VAS scores will be assessed using separate repeated measures ANOVA model, with the relevant score as the dependent variable for on entire sample with device implanted and position accounted for as levels in the model.

Hip subjects

- Hip Outcome Score Activities of Daily Living (HOOS-ADL) at 6 months* and 12 months*

Study Protocol—Device	 smith&nephew
Prospective, Multicenter, Post-Market Clinical Follow-up Study to evaluate safety and performance of the SUTUREFIX ULTRA and SUTUREFIX CURVED Suture Anchors in shoulder and hip arthroscopic repair	Number: 17-5010-06
	Version: 1.0, 09/MAY/2018
	Page: Page 49 of 87

- Modified Harris Hip Score (HHS) at 6 months* and 12 months*
 - The HOOS and HHS scores at different time points and end of study will be will be summarized for the entire sample and device implanted using median, SD, minimum, and maximum. A one sample t-test will be used to test the difference between baseline and end of study scores.

Shoulder subjects

- ROWE Shoulder Scores at 6 months* and 12 months*
- ASES Shoulder Scores at 6 months* and 12 months*
- Complete Constant-Murley Score for shoulder* at 6 months* and 12 months*
 - The ROWE and Constant-Murley Shoulder scores at different time points and end of study will be will be summarized for the entire sample and device implanted using mean, median, SD, minimum, and maximum. A one sample t-test will be used to test the difference between baseline and end of study scores. A non-parametric test will be considered if necessary.

**Patient Reported Outcomes (PROs) are optional and used according to the surgeon's preference*

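### The EQ-5D repeated-measures model names no baseline adjustment, visit list or factor-by-visit term, so its device and position effects carry pre-operative differences between non-randomised groups

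*Combined protocol and SAP*

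**What the plan says.** Section 10.4.2 plans one repeated measures ANOVA for the utility and another for the EQ VAS. It describes the model only as one "with the relevant score as the dependent variable for on entire sample with device implanted and position accounted for as levels in the model". Device and position are the only factors named. The sentence does not list the visits in the response, and mentions neither a visit term, nor an interaction of visit with device or position, nor the pre-operative score as a covariate.

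The surrounding text points two ways on the visits. Just before the model, the scores "will be summarized at baseline and all post-operative visits for the entire sample", which includes the pre-operative value. The endpoint itself is listed as "EQ-5D Questionnaire at 6 months* and 12 months", which does not.

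A pre-operative score is scheduled. Section 9.1.2 has "Complete EQ-5D questionnaire for all subjects" at Visit 1, though patient-reported outcomes are optional at the surgeon's preference. Its planned uses are descriptive ("The change in EQ-5D-5L index utility score and the change in EQ VAS score between baseline and all post-op visits will also be summarised") or a within-sample test ("A one sample t-test will be used to test the difference between baseline and end of study scores"). Neither is a modelled comparison of devices or joints.

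On allocation, section 8.2 states: "This study is an open-label study with consecutive enrolment without randomization".

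**The concern.** No rule assigns the ULTRA or CURVED device, and hip and shoulder subjects enter on different conditions (section 7.2: femoroacetabular impingement versus recurrent dislocation or subluxation). The EQ-5D-5L in section 21.3 opens with walking about, so the two joints could well differ before surgery. A model of the raw score with device and position as factors, and nothing else, cannot separate such a difference from anything that happens after surgery.

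The data are meant to support CE Mark certification (section 8.1), and section 10.1 reads all models at the 5% level. A difference that existed before the operation could be reported as a device or joint finding. If the pre-operative score is also part of the response, a real post-operative difference would be understated as well.

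**Working it through.** The plan gives no figure for this model. The sample-size statement in section 11 concerns the success rate only, so there is nothing to reproduce here.

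**Inputs from the document.** EQ-5D is scheduled at three points: pre-operative, 6 months and 12 months. The response is the raw score. The named factors are device and position. There is no randomisation.

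**Assumed, because the document gives no values.** b is the pre-operative group difference. d is a constant post-operative effect. r is the within-subject correlation. SDs are equal across visits and data are complete. g is the group difference seen at each post-operative visit. Two patterns are considered: the baseline gap persists, g = b + d; or it shrinks by r, g = rb + d.

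**Step 1: formulas.** A main effect with no interaction is the average of the visit-specific differences.
- Three visits in the response: (b + 2g)/3. This is b + 2d/3 if the gap persists, and b(1 + 2r)/3 + 2d/3 if it shrinks.
- 6 and 12 months only, no covariate: g, that is b + d or rb + d.
- 6 and 12 months with the pre-operative score as covariate: g - rb, that is b(1 - r) + d or d.
- Change from baseline, or group-by-visit contrasts against baseline: g - b, that is d or d - b(1 - r).

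**Step 2: numbers at r = 0.5.**

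| Scenario | g | Three visits | 6/12 months only | 6/12 with covariate | Change |
|---|---|---|---|---|---|
| b = -0.10, d = 0, gap persists | -0.10 | -0.100 | -0.100 | -0.050 | 0.000 |
| b = -0.10, d = 0, gap shrinks | -0.05 | -0.067 | -0.050 | 0.000 | +0.050 |
| b = 0, d = 0.05 | 0.05 | 0.033 | 0.050 | 0.050 | 0.050 |

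**Step 3: range for r from 0.3 to 0.7, with b = -0.10 and d = 0.**
- Gap persists: three visits stays at -0.10, and the covariate model leaves -0.10 × (1 - r) = -0.07 to -0.03.
- Gap shrinks: three visits gives -0.10 × (1 + 2r)/3 = -0.053 to -0.080, 6/12 months only gives -0.03 to -0.07, the covariate model gives 0, and change gives +0.07 to +0.03.

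**Step 4: simulation** (assumed: 80 subjects, 25% in one group, SD 0.20, r = 0.5; 8,000 data sets).
- Gap of -0.10 shrinking, no effect: -0.067 (three visits), -0.050 (6/12 only) and 0.000 (with covariate). Rejection rates at 5% were about 36%, 20% and 5%.
- Gap of -0.10 persisting, no effect: -0.101 (three visits) and -0.051 (with covariate).
- No gap, d = 0.05: 0.032 (three visits) and 0.049 (with covariate). Rejection rates were about 12% and 27%.

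A further run of 4,000 data sets under the same assumptions gave empirical standard errors of 0.043 for the three-visit main effect and 0.037 to 0.039 with the covariate.

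Random-intercept models on 4,000 simulated subjects agree in pattern. With b = 0.05 persisting and d = 0, the estimates were 0.044 for three visits, 0.044 for 6/12 months only, 0.022 with the covariate and 0.000 for change.

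**The case against.** The model sentence names no visits. The phrase that includes baseline belongs to the summary tables, and the endpoint list is 6 and 12 months, so a post-operative-only response is open on the text. A reader might infer that the plan's EQ-5D effects are diluted by a third. The document does not support that as a finding: the exact third needs three complete, equally weighted visits and a main effect read without a visit interaction. Optional questionnaires, and EQ-5D at unscheduled visits (section 9.1.6), would change the fraction. Naming no interaction is also not the same as excluding one; group-by-visit contrasts against baseline would not be diluted. This part of the objection stands.

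A reader might also infer that adding the pre-operative score as a covariate clears baseline differences. That holds only if the gap shrinks after surgery to r times its size. If it persists, which is plausible for hip against shoulder, b(1 - r) remains. This stands too.

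The plan limits what the model can support. The study is non-comparative (section 8.4), all tests are exploratory and unpowered (section 10.1), baseline scores are tabulated by device and position, and section 10 defers detail to a SAP to be finalised before database lock. In the assumed setting, the 0.016 between 0.034 and 0.050 (the estimates of a true 0.05 in the 4,000-data-set run) is small against standard errors of 0.037 to 0.043. All this lowers the priority. It does not remove the point: section 8.4 relies on models adjusting for potential confounders, and this model names no adjustment for the obvious one, which is already scheduled.

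**Conclusion.** The point holds as under-specification of an exploratory secondary model. With the raw score as response and no baseline term, device and position main effects carry pre-operative differences under either reading of the visits, to the extent that those differences last beyond surgery. For an assumed gap of -0.10 and r = 0.5, the spurious effect is -0.067 to -0.10 with three visits and -0.05 to -0.10 with the post-operative visits only.

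The dilution to 2d/3 is conditional on the pre-operative score being one of three equally weighted responses and on main effects being read without an interaction. It is zero if only the 6- and 12-month scores are modelled. The gap, SD, correlation and group split are all assumptions. Priority: minor.

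**What to change.** In section 10.4.2, and in the SAP that follows it:
- State that the response is the scheduled 6- and 12-month score.
- Fit the pre-operative score as covariate, with visit, device, position, device-by-visit and position-by-visit terms.
- Report device and position contrasts at each post-operative visit, and describe them as exploratory.
- As a sensitivity analysis, report the same contrasts in change from baseline. The two analyses are exact under opposite assumptions: change if the gap persists, the covariate model if it shrinks by r. Where they disagree, the result depends on how baseline is handled and should be reported so.

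The cost is wording only, since the pre-operative EQ-5D is already scheduled. There is one small downside: because the questionnaire is optional, subjects without a pre-operative score drop out of the adjusted model. A likelihood-based model that keeps all visits and reads group-by-visit contrasts avoids that loss.

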3.4 LIST OF ABBREVIATIONS

Abbreviation	Definition
ADE	Adverse Device Effect(s)
AE	Adverse Event(s)
ASES	American Shoulder and Elbow Surgeons Shoulder Score
BSI	British Standards Institute
CAPA	Corrective and Preventive Action
CE	Conformité Européene
CI	Confidence Interval
CRF	Case Report Form(s)
CRO	Contract Research Organization
CT	Computed Tomography
CTA	Clinical Trial Agreement
CV	Curriculum Vitae
DevD	Device Deficiency(ies)
EQ-5D	EuroQol 5D
FAS	Full Analysis Set Population
FDA	Food and Drug Administration
FAI	Femoroacetabular Impingement
FU	Follow-Up
GCP	Good Clinical Practice
HIPAA	Health Information Portability Accountability Act
HHS	Harris Hip Score
HOOS	Hip Disability and Osteoarthritic Outcome Scores
HOOS-ADL	Hip Outcome Score Activities of Daily Living
IB	Investigator Brochure

Suturefix Ultra Suture Anchor Suturefix Curved Suture Anchor	
Prospective, Multicenter, Post-Market 1 year Clinical Follow-up Study to evaluate safety and performance of the SUTUREFIX ULTRA and SUTUREFIX CURVED Suture Anchors in shoulder and hip arthroscopic repair	Number: 17-5010-06
	Version: 1.0, 09/MAY/2018
	Page: Page 14 of 87

Abbreviation	Definition
ICF	Informed Consent Form
ICH	International Conference on Harmonization of Technical Requirements for Registration of Pharmaceuticals for Human Use
ICMJE	International Committee of Medical Journal Editors
IEC	Independent Ethics Committee
IFU	Instructions for Use
IP	Investigational Product
IRB	Institutional Review Board
ISF	Investigator Site File
ITT	Intention to Treat population
MDI	Multi-directional Instability
MITT	Modified Intention-to-treat Population
MRI	Magnetic Resonance Imaging
NA or N/A	Not Applicable
PI	Principal Investigator
PP	Per-protocol Population
PRO	Subject Report Outcome
ROWE	ROWE Shoulder Score for Instability
S&N	Smith & Nephew
SADE	Serious Adverse Device Effect(s)
SAE	Serious Adverse Event(s)
SAF	Safety population
SAP	Statistical Analysis Plan
SD	Standard Deviation
SLAP	Superior Labrum Anterior-Posterior
USADE	Unanticipated Serious Adverse Device Effect(s)

Suturefix Ultra Suture Anchor	
Suturefix Curved Suture Anchor	
Prospective, Multicenter, Post-Market 1 year Clinical Follow-up Study to evaluate safety and performance of the SUTUREFIX ULTRA and SUTUREFIX CURVED Suture Anchors in shoulder and hip arthroscopic repair	

Abbreviation	Definition
VAS	Visual Analogue Scale

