8.3.2 Secondary Endpoints

- Clinical success rate, defined as subjects without signs of failure and/or re-intervention at 12 months, as assessed by the surgeon
- Intra-operative anchor deployment success rate
- Number of anchors pulled out
- Use of additional anchors as a result of intra-operative failure
- Device-related re-intervention
- Safety evaluation at all time points
- Post-operative clinical success rate and performance assessed with subject reported outcomes as follows:

All subjects:

- Subject pain assessment with VAS at 6 months* and 12 months*
- Subject satisfaction assessment with VAS at 6 months* and 12 months*
- EQ-5D Questionnaire at 6 months* and 12 months*

Suturefix Ultra Suture Anchor Suturefix Curved Suture Anchor	
Prospective, Multicenter, Post-Market 1 year Clinical Follow-up Study to evaluate safety and performance of the SUTUREFIX ULTRA and SUTUREFIX CURVED Suture Anchors in shoulder and hip arthroscopic repair	Number: 17-5010-06 Version: 1.0, 09/MAY/2018 Page: Page 36 of 87

Hip subjects:

- Hip Outcome Score Activities of Daily Living (HOOS-ADL) at 6 months* and 12 months*
- Modified Harris Hip Score (HHS) at 6 months* and 12 months*

Shoulder subjects:

- ROWE Shoulder Scores at 6 months* and 12 months*
- ASES Shoulder Scores at 6 months* and 12 months*
- Constant-Murley Shoulder Scores at 6 months* and 12 months*

** Patient Reported Outcomes (PROs) are optional and used according to the surgeon's preference*

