21.4 ADDITIONAL ASSESSMENTS

Patient Hip Assessments

Pain Assessment

1. Please select a number from the scale below that indicates the level of pain you are experiencing from your hip today

[figure not shown]

*Please comment below

*Please provide a reason for your score _____

Patient Satisfaction

2. Please select a number from the scale below that indicates your level of satisfaction with the arthroscopy repair surgery to stabilize your hip

*Please comment below

*Please provide a reason for your score _____

Study Protocol—Device

Prospective, Multicenter, Post-Market Clinical Follow-up Study to evaluate safety and performance of the SUTUREFIX ULTRA and SUTUREFIX CURVED Suture Anchors in shoulder and hip arthroscopic repair

[figure not shown]
Number: 17-5010-06

Version: 1.0, 09/MAY/2018

Page: Page 70 of 87

Patient Shoulder Assessments**Pain Assessment**

1. Please select a number from the scale below that indicates the level of pain you are experiencing from your shoulder today

*Please provide a reason for your score _____

Patient Satisfaction

2. Please select a number from the scale below that indicates your level of satisfaction with the arthroscopy repair surgery to stabilize your shoulder

*Please provide a reason for your score _____

Study Protocol—Device	 smith&nephew
Prospective, Multicenter, Post-Market Clinical Follow-up Study to evaluate safety and performance of the SUTUREFIX ULTRA and SUTUREFIX CURVED Suture Anchors in shoulder and hip arthroscopic repair	Number: 17-5010-06
	Version: 1.0, 09/MAY/2018
	Page: Page 71 of 87

Hip dysfunction and Osteoarthritis Outcome Score (HOOS), English version LK 2.0

1

HOOS HIP SURVEY

Today's date: _____ / _____ / _____ Date of birth: _____ / _____ / _____

Name: _____

INSTRUCTIONS: This survey asks for your view about your hip. This information will help us keep track of how you feel about your hip and how well you are able to do your usual activities.

Answer every question by ticking the appropriate box, only one box for each question. If you are uncertain about how to answer a question, please give the best answer you can.

Symptoms

These questions should be answered thinking of your hip symptoms and difficulties during the **last week**.

S1. Do you feel grinding, hear clicking or any other type of noise from your hip?

Never	Rarely	Sometimes	Often	Always
				

S2. Difficulties spreading legs wide apart

None	Mild	Moderate	Severe	Extreme

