				

S3. Difficulties to stride out when walking

None	Mild	Moderate	Severe	Extreme
				

Stiffness

The following questions concern the amount of joint stiffness you have experienced during the **last week** in your hip. Stiffness is a sensation of restriction or slowness in the ease with which you move your hip joint.

S4. How severe is your hip joint stiffness after first wakening in the morning?

None	Mild	Moderate	Severe	Extreme
				

S5. How severe is your hip stiffness after sitting, lying or resting later in the day?

None	Mild	Moderate	Severe	Extreme
				

Pain

P1. How often is your hip painful?

Never	Monthly	Weekly	Daily	Always
				

What amount of hip pain have you experienced the **last week** during the following activities?

P2. Straightening your hip fully

None	Mild	Moderate	Severe	Extreme
				

Study Protocol—Device	
Prospective, Multicenter, Post-Market Clinical Follow-up Study to evaluate safety and performance of the SUTUREFIX ULTRA and SUTUREFIX CURVED Suture Anchors in shoulder and hip arthroscopic repair	Number: 17-5010-06
	Version: 1.0, 09/MAY/2018
	Page: Page 72 of 87

Hip dysfunction and Osteoarthritis Outcome Score (HOOS), English version LK 2.0

2

What amount of hip pain have you experienced the **last week** during the following activities?

P3. Bending your hip fully

None	Mild	Moderate	Severe	Extreme
				

P4. Walking on a flat surface

None	Mild	Moderate	Severe	Extreme
				

P5. Going up or down stairs

None	Mild	Moderate	Severe	Extreme
				

P6. At night while in bed

None	Mild	Moderate	Severe	Extreme
				

P7. Sitting or lying

None	Mild	Moderate	Severe	Extreme
				

P8. Standing upright

None	Mild	Moderate	Severe	Extreme
				

P9. Walking on a hard surface (asphalt, concrete, etc.)

None	Mild	Moderate	Severe	Extreme
				

P10. Walking on an uneven surface

None	Mild	Moderate	Severe	Extreme
				

Function, daily living

The following questions concern your physical function. By this we mean your ability to move around and to look after yourself. For each of the following activities please indicate the degree of difficulty you have experienced in the **last week** due to your hip.

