Hip dysfunction and Osteoarthritis Outcome Score (HOOS), English version LK 2.0

4

Function, sports and recreational activities

The following questions concern your physical function when being active on a higher level. The questions should be answered thinking of what degree of difficulty you have experienced during the **last week** due to your hip.

SP1. Squatting

None	Mild	Moderate	Severe	Extreme
				

SP2. Running

None	Mild	Moderate	Severe	Extreme
				

SP3. Twisting/pivoting on loaded leg

None	Mild	Moderate	Severe	Extreme
				

SP4. Walking on uneven surface

None	Mild	Moderate	Severe	Extreme
				

Quality of Life

Q1. How often are you aware of your hip problem?

Never	Monthly	Weekly	Daily	Constantly
				

Q2. Have you modified your life style to avoid activities potentially damaging to your hip?

Not at all	Mildly	Moderately	Severely	Totally
				

Q3. How much are you troubled with lack of confidence in your hip?

Not at all	Mildly	Moderately	Severely	Extremely
				

Q4. In general, how much difficulty do you have with your hip?

None	Mild	Moderate	Severe	Extreme
				

Thank you very much for completing all the questions
in this questionnaire.

Study Protocol—Device	
Prospective, Multicenter, Post-Market Clinical Follow-up Study to evaluate safety and performance of the SUTUREFIX ULTRA and SUTUREFIX CURVED Suture Anchors in shoulder and hip arthroscopic repair	Number: 17-5010-06
	Version: 1.0, 09/MAY/2018
	Page: Page 75 of 87

Modified Harris Hip Score (mHHS) Calculation SOURCE WORKSHEET

Clinician Name:	
Subject ID:	_____ - _____
Subject Code:	_____ - _____
Date (DD/MMM/YYYY):	

Instructions:

Use this Work Instruction as source documentation for the total mHHS calculation (mHHS question 12). The total mHHS is considered NULL if any question 1-8 is missing. mHHS questions 9-11 are not included in the total mHHS calculation.

Enter the actual score for questions 1-8 that correlates to the study subject's mHHS questionnaire response. To obtain the total mHHS add the actual scores from questions 1-8 then multiply by 1.1.

[figure not shown]
[figure not shown]
Question	Possible Score	Actual Score
1. Hip Pain:		
none or ignores it	44	
slight, minimal; no compromise in activities	40	
mild; following longer activities	30	

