moderate; some limitations of activities	20	
marked; serious limitations of activities	10	
Disabled; no activities possible, bedridden	0	
2. Enter public transportation:		
yes, possible	1	
no, unable	0	
3. Putting on shoes and socks:		
with ease	4	
with difficulty	2	
unable	0	
4. Distance walked:		
unlimited, several hours	11	
six blocks, up to 2 km/1 mile	8	
daily shopping, up to 500 km/.3 miles	5	
indoors only, up to 50 m/150 feet	2	
bed / chair / not able to walk	0	

Question	Possible Score	Actual Score
5. Support:		
None	11	
single cane for long walk	7	
single cane most of the time	5	
one crutch	3	
two canes	2	
two crutches or not able to walk	0	
6. Stairs:		
foot over foot, without banister	4	
foot over foot, with banister	2	
in a manner	1	
unable	0	
7. Sitting:		
comfortably in any chair for one hour	5	
comfortably on high chair for one-half hour	3	
unable to sit comfortably	0	
8. Limp:		
none	11	
slight	8	
moderate	5	
severe	0	
Questions 1-8 Total:		
Total mHHS (Questions 1-8 Total x 1.1):		

Study Protocol—Device

Prospective, Multicenter, Post-Market Clinical Follow-up Study to evaluate safety and performance of the SUTUREFIX ULTRA and SUTUREFIX CURVED Suture Anchors in shoulder and hip arthroscopic repair

Number: 17-5010-06
Version: 1.0, 09/MAY/2018
Page: Page 76 of 87

 SHOULDER ASSESSMENT FORM AMERICAN SHOULDER AND ELBOW SURGEONS		
PATIENT SELF-EVALUATION		
Are you having pain in your shoulder? (circle correct answer)	Yes	No
Mark where your pain is on this diagram:		
Do you have pain in your shoulder at night?	Yes	No
Do you take pain medication (aspirin, Advil, Tylenol, etc.)?	Yes	No
Do you take narcotic pain medication (codeine or stronger)?	Yes	No
How many pills do you take each day (average)?	pills	
How bad is your pain today (mark line)?		
No pain at all	Pain as bad as it can be	
Does your shoulder feel unstable (as if it is going to dislocate?)	Yes	No
How unstable is your shoulder (mark line)?		
Very stable	Very unstable	
Circle the number in the box that indicates your ability to do the following activities: 0 = Unable to do; 1 = Very difficult to do; 2 = Somewhat difficult; 3 = Not difficult		
ACTIVITY	RIGHT ARM	LEFT ARM
1. Put on a coat	0 1 2 3	0 1 2 3
2. Sleep on your painful or affected side	0 1 2 3	0 1 2 3
3. Wash back/do up bra in back	0 1 2 3	0 1 2 3
4. Manage toileting	0 1 2 3	0 1 2 3
5. Comb hair	0 1 2 3	0 1 2 3
6. Reach a high shelf	0 1 2 3	0 1 2 3
7. Lift 10 lbs. above shoulder	0 1 2 3	0 1 2 3

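### The appended Constant and modified Harris Hip sheets contain category errors, and ASES is missing from the sentence that sets out the shoulder-score analysis

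*Combined protocol and SAP*

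**What the plan says.** Section 8.3.2 lists five joint-specific scores at 6 and 12 months, all left to the surgeon's choice: two for the hip (HOOS-ADL, modified Harris Hip) and three for the shoulder (ROWE, ASES, Constant-Murley). The forms are in Appendix 21.4.

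- **Constant sheet.** It asks for a single answer to each question. Forward flexion and lateral elevation each offer five boxes, the lowest being 31-60 degrees. Every external-rotation option has the hand at the head or the arm fully raised.
- **Modified Harris Hip worksheet.** The rule is explicit: "To obtain the total mHHS add the actual scores from questions 1-8 then multiply by 1.1". The walking band worth 5 points is labelled "daily shopping, up to 500 km/.3 miles".
- **Shoulder analysis.** Section 10.4.2 lists all three shoulder scores. The sentence that sets out the summary begins "The ROWE and Constant-Murley Shoulder scores at different time points and end of study", and the baseline-to-end t-test follows from it. ASES is not named.
- **Hip score.** The endpoint is "Hip Outcome Score Activities of Daily Living (HOOS-ADL) at 6 months* and 12 months". The abbreviation list expands HOOS as "Hip Disability and Osteoarthritic Outcome Scores". The appended form is the "Hip dysfunction and Osteoarthritis Outcome Score (HOOS), English version LK 2.0", which includes a section headed "Function, daily living". The analysis sentence reads "The HOOS and HHS scores at different time points and end of study will be will be summarized for the entire sample".

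**The concern.** An endpoint score is only as good as the form it is read from. If a form has no box for the worst state, or a band label contradicts itself, the error enters the source record, and no later analysis plan can take it out. On the Constant sheet the loss falls on the poorest outcomes, which is the wrong place to lose information in a study meant to support performance. On the hip worksheet a rater working in metric units meets a band that makes no sense as printed, and the sites are European.

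The ASES gap is different in kind. The data would be collected correctly, but the plan does not commit to the summary and test that it gives the other two shoulder scores, so how ASES is reported is left open. The hip naming conflict is an editorial loose end of the same sort.

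**Working it through.** The plan states no figure to reproduce here. The check compares forms with text, plus some arithmetic.

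**1. Constant sheet (Appendix 21.4).** The boxes for forward flexion and lateral elevation are 31-60, 61-90, 91-120, 121-150 and 151-180.

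- Whole degrees from 0 to 180: 181. Covered, 31 to 180: 150. Not covered: 181 - 150 = 31, namely 0 to 30.
- External rotation: five options, none below the head. Item 3 (arm positioning) accepts a subject who reaches only the waist, so the form admits a subject for whom external rotation has no true answer.
- Internal rotation starts at the lateral thigh and strength starts at 0, so the sheet does provide low categories elsewhere. Three of the four range-of-motion items lack one.
- Direction of error: upgrading to the lowest printed box raises the score. Leaving a blank that removes the subject's total raises the group mean, because a poor result drops out. A blank scored as zero would do no harm, but no such rule is given. The sheet prints no point values, so the size per item cannot be worked out from the documents.

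**2. Modified Harris Hip worksheet (Appendix 21.4).** Converting the imperial half of each label:

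| Points | Metric label | Imperial label | Imperial converted |
|---|---|---|---|
| 8 | 2 km | 1 mile | 1 x 1.609 = 1.61 km |
| 5 | 500 km | 0.3 mile | 0.3 x 1.609 = 0.48 km |
| 2 | 50 m | 150 feet | 150 x 0.3048 = 45.7 m |

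- Only the 5-point row disagrees with itself: 500 / 0.48 is about 1,000-fold. In metric terms it also exceeds the 8-point band, so the order breaks.
- One band: (8 - 5) x 1.1 = 3.3 points. Upper bound, if a subject with unlimited walking were placed in the 5-point band: (11 - 5) x 1.1 = 6.6 points.
- The rest of the sheet is coherent: 44 + 1 + 4 + 11 + 11 + 4 + 5 + 11 = 91, and 91 x 1.1 = 100.1. It also has a missing-item rule.

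**3. ASES.** Shoulder scores listed in 8.3.2 and 10.4.2: three. Named in the summary-and-test sentence: two. Section 10.1 promises listings and suitable summary statistics for all secondary endpoints, so ASES keeps a generic summary but has no planned baseline comparison. The form rates right and left arms separately, and no text says which is analysed.

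**4. Hip score.** Items on the appended form: 5 symptom and stiffness + 10 pain + 17 daily living + 4 sport + 4 quality of life = 40. The daily-living section is A1-A17, 17 of the 40. The instrument that the endpoint needs is therefore present. What is missing is a single name and a statement that these 17 items form the endpoint.

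**The case against.** The best case against raising this is that the scores are optional, secondary and exploratory in an unpowered study, and that section 10 defers detail to a later SAP. That carries weight on severity. It also means that the ASES and hip wording could be settled there. It does not help the two sheets: a SAP written before database lock cannot recover a motion grade that had no box.

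Second, the table text should be confirmed on the printed page, since text taken from a PDF can lose a box or alter a unit. That is fair and belongs in the fix. The neighbouring bands read cleanly, and both elevation items run without a break from 31 to 180.

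Third, hardly anyone would read the walking band literally, because the mile figure and the adjacent bands show the intended order. I accept this. The 3.3 points is the price of a misreading that is possible but unlikely, not an expected error.

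Fourth, correcting the categories leaves other scoring gaps. The Constant and ROWE sheets print no points and the ASES form gives no composite formula. This is true, but those rules can be supplied later without loss of data.

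A reader might infer more than the documents support:

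- *That ASES has no analysis.* Section 10.1 covers it generically.
- *That the hip endpoint uses the wrong instrument or could mean several quantities.* The daily-living section is on the form, and in 10.4.2 the short form HOOS stands beneath the HOOS-ADL entry and reads as shorthand, as HHS does for the modified score.
- *That collecting the other 40 - 17 = 23 items is a fault.* Giving a whole questionnaire and analysing one section is not an error, and summarising the rest is a preference.
- *That many shoulders are too stiff to score.* The remark on stiffness in section 4.1 concerns SLAP repair and allows up to 6 months to regain motion. The first postoperative score is at 6 months, and the shoulder group is defined by recurrent dislocation or subluxation.

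**Conclusion.** The point holds as a minor one. Two source sheets are wrong as printed: three Constant motion items have no lowest category, and one Harris Hip band carries a metric label that contradicts its own mile figure. ASES is a listed endpoint left out of the sentence that gives its companions a summary and a test. The hip score needs consistent naming only.

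The Constant error would push scores upward, in probably few subjects. That direction assumes that affected items are upgraded or the total is lost, and the documents give neither a count nor a rule for blanks. The Harris Hip label is worth 3.3 points per misplaced band if it is misread at all. The conclusions about both sheets rest on the form text matching the printed page. The primary endpoint and the sample size do not depend on any of this.

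**What to change.** - **Constant sheet:** after checking the printed page, add a lowest category to forward flexion, lateral elevation and external rotation, consistent with the version of the instrument in use, before the form is first used.
- **Modified Harris Hip worksheet:** correct the metric half of the 5-point walking label so that it agrees with 0.3 mile.
- **Section 10.4.2:** add ASES, specified as the operated arm, to the sentence that gives the shoulder summary and baseline-to-end test.
- **Sections 8.3.2 and 10.4.2:** name the hip endpoint as HOOS LK 2.0, daily-living section, items A1-A17, in place of the present long name and the bare HOOS. Summaries of the other sections are optional.

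The cost is wording in two sections, corrections to two worksheets, and a few table rows for ASES. There is no new assessment and no added burden on subjects.
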